3.3.2 Events of Secondary patency of target lesions and termination

Secondary patency of a target lesion is defined as the period after index procedure until reaching one of the following conditions at the earliest. In the event “VIABAHN occlusion”, if the follow-up date for “Loss of Patency (██████████)” as the answer to the question “Did the device implanted in a treated lesion maintain patency? (██████████)” and onset date █████ or outcome date (██████████) of “recovered (██████████)” or “relived (██████████)” adverse event “Occlusion of VIABAHN” as the answer to “Outcome (██████████)” are the same, the event is not treated as an event.

Event	EDC Item	Event date
Occlusion of VIABAHN	
After answering “Loss of Patency (██████████)” to “Did the device implanted in a treated lesion maintain patency? (██████████)”, answer to the question “Did the device implanted in a treated lesion maintain patency? (██████████)” is not “Patency (██████████)” as well as “Recovered (██████████)” or “Relived (██████████)” adverse event “Occlusion of VIABAHN” is not entered in “Outcome (██████████)”. 
 
“Occlusion of VIABAHN” is entered in “Adverse event (██████████)” and “Outcome (██████████)” of adverse event “Occlusion of VIABAHN” is either “Unrecovered (██████████)” or “Death (██████████)” or “Unknown (██████████)”, and the answer to the subsequent question “Did the device implanted in a treated lesion maintain
	
Follow-up date of “Loss of Patency (██████████) (██████████) (██████████)”
 
Onset date (██████████)

Event	EDC Item	Event date
	patency? (██████████) ” is not “Patency (██████████) ████” as well as “Recovered (██████████) ” or “Relived (██████████) ” adverse event “Occlusion of VIABAHN” is not entered in “Outcome (██████████) ”.	
Discontinuation of study	Answer to “Did conduct follow-up (██████████) ” is “Discontinuation (F██████████) ” and “Reason for discontinuation (F██████████) ” is “Other (discontinuation of use of the device, etc. (██████████) ”	Date determined to be discontinued (██████████)
	Answer to “Did complete the study? (██████████) ” is “Discontinuation (██████████) ” and “Reason for discontinuation (██████████) ” is “Other (discontinuation of use of the device, etc. (██████████) ”	Date determined to be discontinued (██████████)

In addition, termination is defined as the latest of the following dates.

Termination	EDC Item	Termination date
Completion of study	Answer to “Did complete the study? (██████████) ” is “Completed (██████████) ” and to “Did the device implanted in a treated lesion maintain patency? (██████████) ” is “Patency (██████████) ”	Date of completion (██████████)
Study ongoing	Date of procedure (██████████)	Date of procedure (██████████)

Termination	EDC Item	Termination date
	
“Occlusion of VIABAHN” is entered in “Adverse event ([REDACTED])” and answer to “Outcome [REDACTED])” of Adverse event
 
“Occlusion of VIABAHN” is “Recovered ([REDACTED])” or “Relived ([REDACTED])”
	
Outcome date ([REDACTED])

	
Answer to “Did the device implanted in a treated lesion maintain patency? [REDACTED]) ” is “Patency ([REDACTED])
	
Date of follow-up ([REDACTED])

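### The adverse-event rule for secondary patency (SAP 3.3.2, repeated in 3.3.4) does not tie a recovery to the occlusion being judged, so an earlier salvaged occlusion can cancel a later permanent one

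*SAP*

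**What the plan says.** SAP 3.3.2 runs secondary patency of the target lesion from the index procedure "until reaching one of the following conditions at the earliest", so the event rows are alternatives. Four parts of the section matter here.

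- **Lead-in exemption.** If the visit date of a Loss of Patency answer and the onset or outcome date of a recovered or relieved occlusion adverse event "are the same, the event is not treated as an event".
- **Row 1 (follow-up answer).** It opens "After answering “Loss of Patency" and counts the loss if patency is not then answered and no recovered or relieved occlusion event is entered. The event is dated at the follow-up visit.
- **Row 2 (adverse-event entry).** An occlusion event counts if its own outcome is unrecovered, death or unknown, "and the answer to the subsequent question “Did the device implanted in a treated lesion maintain" patency is not answered as patent, and a recovered or relieved "adverse event “Occlusion of VIABAHN” is not entered in" the outcome field. The event is dated at onset.
- **Discontinuation.** Stopping the study with the reason "Other (discontinuation of use of the device, etc" is an event whatever the occlusion history.

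If no event is counted, "termination is defined as the latest of the following dates": completion with patency, the procedure date, the outcome date of a recovered occlusion, or a follow-up visit with patency.

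SAP 3.3.4 repeats the row 1 and row 2 wording for the circuit, both for the stent graft and for access occlusion elsewhere. It adds a separate event, discontinuation of the vascular access. Protocol 9.1(2) counts patency regained after re-treatment as patent time.

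**The concern.** Row 2 first requires the judged occlusion's own outcome to be unrecovered, death or unknown. Its last condition, that no recovered or relieved occlusion is entered, can therefore only refer to a different record. Nothing says that record must be later, or that it must describe the same occlusion. The word for subsequent is attached to the patency question alone.

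A patient salvaged early and then permanently occluded has a recovered record on file. A programmer who follows row 2 as written drops the permanent occlusion. A dropped loss becomes a censored observation, so any such error raises the Kaplan-Meier estimate. The patients affected are those with repeated occlusions. Protocol 9.1(2) credits patency regained after re-treatment, but it does not say that one salvage protects against a later permanent failure.

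**Working it through.** The documents state no figure that tests this rule, so there is nothing to reproduce. The check has two parts: the rule applied to a test patient, then an illustration of size.

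**1. Test patient.** Patent at visits on days 30, 90 and 180. Occlusion event on day 120, recovered on day 121. Permanent occlusion on day 300. Three readings of 3.3.2:

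- A: the recovery clause carries no date condition in either row.
- B: row 1 is in time order, row 2 has no date condition.
- C: both rows are in time order.

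| How the permanent loss is recorded | A | B | C |
|---|---|---|---|
| Adverse event day 300 and Loss of Patency day 365 | censored 180 | event 365 | event 300 |
| Adverse event day 300 only | censored 180 | censored 180 | event 300 |
| Loss of Patency day 365 only | censored 180 | event 365 | event 365 |
| Adverse event day 300, then discontinuation for the other reason day 310 | event 310 | event 310 | event 300 |

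The lead-in exemption does not apply, because day 365 matches neither day 120 nor day 121. The censoring date is the latest of day 0, day 121 and day 180.

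Under B the loss disappears only when no visit records it and no discontinuation row applies; otherwise it is delayed. Delay can also matter. Protocol Table 2 allows the 24-month visit on days 640 to 820, while SAP 4.4.2.4 ends the 24-month Kaplan-Meier range at day 730. Under B, a permanent occlusion on day 500 that is first recorded at a visit on day 740 is missing from the 24-month estimate.

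**2. Size under reading A, fixed numbers of losses.** N = 100 is the target in protocol section 3. The rest is assumed: E = 10, 20 or 30 permanent occlusions by 24 months, k of them cancelled (about 10% to 50%), cancelled patients censored at 60% of their event time, no other censoring, and no recapture by other rows. True patency is (100 − E)/100. The reported value must lie between (100 − E)/(100 − k), if cancelled patients leave at day 0, and (100 − E + k)/100, if they stay at risk to the end.

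| E | k | True % | Bounds % | Simulated % | Bias, points |
|---|---|---|---|---|---|
| 10 | 1 | 90.0 | 90.9 to 91.0 | 90.9 | +0.9 |
| 10 | 5 | 90.0 | 94.7 to 95.0 | 94.8 | +4.8 |
| 20 | 2 | 80.0 | 81.6 to 82.0 | 81.7 | +1.7 |
| 20 | 10 | 80.0 | 88.9 to 90.0 | 89.2 | +9.2 |
| 30 | 3 | 70.0 | 72.2 to 73.0 | 72.3 | +2.3 |
| 30 | 15 | 70.0 | 82.4 to 85.0 | 83.0 | +13.0 |

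**3. Cross-check with recurrent occlusions.** Assume occlusions at a constant rate r per year, each salvaged with probability s.

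- True 24-month patency is exp(−2r(1 − s)).
- Losses with no earlier salvage, the only ones reading A keeps, have probability (1 − s)(1 − exp(−2r)).

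With r = 0.5 and s = 0.8, true patency is exp(−0.2) = 81.9%. Losses kept are 0.2 × (1 − exp(−1)) = 12.6%, against 18.1% in all, so 1 − 12.6/18.1 = 30% are cancelled. Reported patency is 100 − 12.6 = 87.4% if cancelled patients stay at risk to the end, or 87.1% if they are censored at the loss. The bias is about 5.3 to 5.5 points.

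Over r = 0.3 to 0.8 and s = 0.7 to 0.9, the cancelled share is 18% to 46%. The bias is 1.3 to 13.0 points with censoring at the loss, and up to 14.2 if cancelled patients stay at risk.

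**The case against.** The strongest reply is that the section as a whole points to a reading in time order, under which there is no bias. Row 1 opens with a phrase that naturally governs both halves of its condition. The lead-in exemption carries an explicit same-date condition. If any recovered record already cancelled every Loss of Patency answer, that exemption would have no work to do. The English is also plainly a translation, so the placement of one adverb is thin evidence of intent.

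This stands for row 1. It does not repair row 2: the lead-in compares the date of a follow-up answer, which is row 1 material, and adds an exemption without limiting row 2. The author may have meant a later record showing that the same occlusion was resolved, but row 2 does not say so.

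A reader might infer that the exemption has no date condition anywhere, that any recovered occlusion cancels every later one, and that both secondary patency endpoints are therefore overstated. The documents do not support that. A Loss of Patency answer can still count under row 1, and discontinuation for the other reason always counts. In 3.3.4 a patient whose access is abandoned has an event whatever the adverse-event history, at most at a shifted date, which fits protocol 9.1(4).

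These backstops are partial for the target lesion. Row 1 needs a visit that records the loss, the discontinuation row needs the patient to leave the study for that reason, and 3.3.2 has no event for discontinued access.

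**Conclusion.** The point holds for row 2 of the stent-graft occlusion event in SAP 3.3.2 and for the repeated wording in 3.3.4. Followed literally, the rule lets an earlier salvaged occlusion cancel a later permanent one, and any resulting error favours the device. The exposure is mainly in secondary patency of the target lesion; the circuit endpoint is largely protected.

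Whether secondary patency will in fact be overstated depends on how the rule is programmed and on how many patients have a salvaged and then a permanent occlusion. The documents give no figure for the latter. The range of about 1 to 13 points at 24 months rests on assumed inputs, the reading with no date condition in either row, and no recapture by other rows. It is an upper-end illustration for the target lesion and should not be carried over to the circuit. If row 1 is in time order and only row 2 is not, the effect is smaller; if both are in time order, it is zero. The text should be corrected, because it states a rule that gives a wrong classification when followed as written.

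**What to change.** State in SAP 3.3.2 and 3.3.4 that an occlusion is cancelled only by a Patency answer dated after it, or by a recovered or relieved outcome of that same occlusion, and that a recovered record of an earlier, separate occlusion does not cancel a later one. In 3.3.4 apply this to both occlusion types.

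For row 1, match each Loss of Patency answer to the occlusion record it reports. Do not require the outcome date to fall on or after the visit date. Row 1 dates the loss at the visit, so an occlusion already salvaged before that visit would fail such a test and, without a later Patency answer, would be counted as permanent.

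This gives the classification under reading C. The cost is one sentence in each section and a record-link condition in the program. No new data item is needed if answers and occlusion records can be matched from existing entries.

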3.3.3 Events of primary patency of vascular access circuit and termination

Primary patency of vascular access circuit is defined as the period after index procedure until reaching one of the following conditions at the earliest. (If “Date of vascular access discontinuation” is entered, it is judged within the period up to the date of the discontinuation)

Evet	EDC Item	Date of Event
VIABAHN [REDACTED] Occlusion of VIABAHN	Answer to “Did the device implanted in a treated lesion maintain patency? [REDACTED])” is “Loss of patency [REDACTED]”	Date of follow-up ([REDACTED])
	[REDACTED] [REDACTED] “Occlusion of VIABAHN” is entered in “Adverse Event [REDACTED]”	Date of onset ([REDACTED])
Occlusion of vascular access	Answer to “Vascular access maintain patency? [REDACTED])” is Loss of patency [REDACTED]	Date of follow-up ([REDACTED])
	Enter “Occlusion of vascular access (Other than treated lesion)” in “Adverse Event [REDACTED]”	Date of onset ([REDACTED])
Conduct reintervention	“Purpose of reintervention [REDACTED])” is “Patency of the initial implanted device [REDACTED]” or “Patency of vascular access circuit (excluding a site of initial implantation of the device) [REDACTED]”	Date of reintervention ([REDACTED])
Discontinuation of study	Answer to “Did conduct follow-up [REDACTED])” is “Discontinuation [REDACTED]” and “Reason for discontinuation [REDACTED])” is “Other (discontinuation of use of the device, etc. [REDACTED])”	Date determined to be discontinued ([REDACTED])
	Answer to “Did complete the study? [REDACTED])” is “Discontinuation [REDACTED]” and “Reason for	Date determined to be discontinued ([REDACTED])

Evet	EDC Item	Date of Event
	discontinuation ([REDACTED])” is “Other (discontinuation of use of the device, etc. [REDACTED])”	
Discontinuation of vascular access	Answer to “Is vascular access used at the time of treatment continuously used? [REDACTED] ” is “No ([REDACTED])”	Date of discontinuation of vascular access used at the time of treatment [REDACTED]

In addition, termination is defined as the latest of the following dates.

Termination	EDC Item	Termination date
Completion of study	Answer to “Did complete the study? ([REDACTED])” is “Completed ([REDACTED])”, to “Did vascular access maintain patency? ([REDACTED])” is “Patency ([REDACTED])”, and to “Did the device implanted in the treated lesion maintain patency? ([REDACTED])” is “Patency ([REDACTED])”.	Date of completion [REDACTED]
Study ongoing	Date of procedure ([REDACTED]) [REDACTED] [REDACTED] [REDACTED] [REDACTED] [REDACTED] [REDACTED] The answer to “Did vascular access maintain patency? ([REDACTED])” is “Maintain patency ([REDACTED])”, and	Date of procedure ([REDACTED]) [REDACTED] Date of follow-up ([REDACTED])

Termination	EDC Item	Termination date
	
to “Did the device implanted in the treated lesion maintain patency?
 
[REDACTED]) ” is “Maintain patency [REDACTED]
	

3.3.4 Events of Secondary patency of vascular access circuit and termination

Secondary patency of a target lesion is defined as the period after index procedure until reaching one of the following conditions at the earliest (If “Date of vascular access discontinuation” is entered, it is judged within the period up to the date of the discontinuation). In the event “VIABAHN occlusion” and “vascular access occlusion”, if the follow-up dates ([REDACTED]) for “Loss of Patency ([REDACTED]) as the answer to the question “Did the device implanted in a treated lesion maintain patency? ([REDACTED])” and “Did vascular access maintain patency (FU.FUVASOPYN)” and onset date ([REDACTED]) or outcome date ([REDACTED]) of “Recovered ([REDACTED])” or “Relived ([REDACTED])” adverse event “Occlusion of VIABAHN” and “Occlusion of vascular access (Other than treated lesion)” as the answer to “Outcome ([REDACTED])” are the same, the event is not handled as an event.

Event	EDC Item	Event date
Occlusion of VIABAHN	After answering “Loss of Patency ([REDACTED]) to “Did the device implanted in the treated lesion maintain patency? ([REDACTED])”, answer to the question “Did the device implanted in the treated lesion maintain patency? ([REDACTED])” is not “Patency ([REDACTED]) as well as “Recovered ([REDACTED])” or “Relived ([REDACTED])” adverse event “Occlusion of VIABAHN” is not entered in “Outcome ([REDACTED])”.	Follow-up date of “Loss of Patency ([REDACTED])
	“Occlusion of VIABAHN” is entered in “Adverse event ([REDACTED])” and “Outcome ([REDACTED])” of adverse event “Occlusion of VIABAHN” is either “Unrecovered ([REDACTED]) “Death ([REDACTED]) or “Unknown ([REDACTED]) and the answer to the subsequent question “Did the device implanted in a treated lesion	Onset date ([REDACTED])

Event	EDC Item	Event date
	
maintain patency?
 
([REDACTED]) is not “Patency
 
([REDACTED] as well as
 
“Recovered ([REDACTED])” or
 
“Relived ([REDACTED])” adverse event “Occlusion of VIABAHN” is not entered in “Outcome ([REDACTED])”.
	
Occlusion of vascular access	
After answering “Loss of Patency ([REDACTED] to “Did vascular access maintain patency? ([REDACTED]”, the answer to the question “Did vascular access maintain patency?
 
([REDACTED] is not “Patency
 
([REDACTED] as well as
 
“Recovered ([REDACTED])” or
 
“Relived ([REDACTED])” adverse event “Occlusion of vascular access (Other than treated lesion) ” is not entered in “Outcome ([REDACTED])”.
	
Follow-up date of “Loss of Patency
 
[REDACTED] [REDACTED]

	
Enter “Occlusion of vascular access (Other than treated lesion) ” in
 
“Adverse event ([REDACTED])” ,
 
“Outcome ([REDACTED])” of
 
“Occlusion of vascular access (Other than treated lesion) ” is either
 
“Unrecovered ([REDACTED])
 
“Death ([REDACTED] or
 
“Unknown ([REDACTED] and the answer to the subsequent question
 
“Did vascular access maintain patency? ([REDACTED]” is not
 
“Patency ([REDACTED] as well as “Recovered ([REDACTED])
	
Onset date
 
([REDACTED])

Event	EDC Item	Event date
	or “Relived ([REDACTED])” adverse event “Occlusion of vascular access (Other than treated lesion)” is not entered in “Outcome ([REDACTED]).	
Discontinuation of study	[REDACTED] Answer to “Did conduct follow-up ([REDACTED])” is “Discontinuation ([REDACTED])” and “Reason for discontinuation ([REDACTED])” is “Other (discontinuation of use of the device, etc. ([REDACTED]))”	Date determined to be discontinued ([REDACTED])
	Answer to “Did complete the study? ([REDACTED])” is “Discontinuation ([REDACTED])” and “Reason for discontinuation ([REDACTED])” is “Other (discontinuation of use of the device, etc. ([REDACTED]))”	Date determined to be discontinued ([REDACTED])
Discontinuation of vascular access	Answer to “Is vascular access used at the time of treatment continuously used? ([REDACTED])” is “No ([REDACTED])”	Date of discontinuation of vascular access used at the time of treatment ([REDACTED])

In addition, termination is defined as the latest of the following dates.

Termination	EDC Item	Termination date
Completion of study	Answer to “Did complete the study? ([REDACTED])” is “Completed ([REDACTED]) and to “Did vascular access maintain patency? ([REDACTED]) is “Patency ([REDACTED])”, to “Did the device implanted in the treated lesion maintain patency? ([REDACTED]) is “Patency ([REDACTED])”	Date of completion ([REDACTED])
調査継続中	[REDACTED]	[REDACTED]

Termination	EDC Item	Termination date
	
Enter “Occlusion of VIABAHN” or “Occlusion of vascular access (Other than treated lesion)” in “Adverse event ()”, and “Recovered ()” or “Relived ()” in “Outcome ()” of each adverse event.
	Outcome date [REDACTED]
	
Answer to “Did vascular access maintain patency?” [REDACTED] is “Patency [REDACTED]” and to “Did the device implanted in the treated lesion maintain patency?” ([REDACTED]) is “Patency [REDACTED]
	Date of completion (FU.FUYDAT)

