4.2 Handling of missing values

4.2.1 Data Complements

For missing data, data complements are not performed.

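### SAP 3.3.4 labels the censoring date for ongoing patent circuits as the completion date, where 3.3.1 to 3.3.3 use the follow-up date; the label should be corrected and the variable confirmed

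*SAP*

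**What the plan says.** SAP 3.3.1 to 3.3.4 define events and censoring (called termination) for the four patency endpoints. In each, the censoring date is the latest of several listed dates; 3.3.4 says "In addition, termination is defined as the latest of the following dates".

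The last termination row applies when the patency questions are answered patent. In 3.3.3, for primary circuit patency, its date is "Date of follow-up ([REDACTED"]). Sections 3.3.1 and 3.3.2 use the same date type. In 3.3.4, for secondary circuit patency, the date is "Date of completion (FU.FUYDAT"). A completion-of-study row, with its own date of completion, already stands higher in the 3.3.4 table.

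The first study-ongoing row of 3.3.4 is redacted and its heading is left in Japanese. In 3.3.3 that row carries "Date of procedure ([REDACTED"]).

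The opening sentence of 3.3.4 names a different endpoint from its heading: "Secondary patency of a target lesion is defined as the period after index procedure until reaching one of the following conditions at the earliest".

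**The concern.** Under the label as printed, 3.3.4 has no visible rule that censors an event-free patient at the last visit where the circuit was seen patent. Completers are covered by their own row. Patients who leave early, or are still in follow-up at a data cut, would be expected to have no completion date. For those who discontinue, the SAP lists a separate date, "Date determined to be discontinued ([REDACTED"]), and in 3.3.4 it appears only as an event date, for one reason for discontinuation. SAP 4.2.1 rules out filling the gap: "For missing data, data complements are not performed".

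Such patients would fall back on an earlier listed date while every observed event stayed in the analysis. The risk sets shrink and the events do not, so the Kaplan-Meier estimate can only fall or stay equal. Someone programming from the label and someone programming from the variable name could also draw different curves for the same endpoint.

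**Working it through.** **Reading the rows side by side**

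| SAP section | Endpoint | Date in the last row (patency answered patent) |
|---|---|---|
| 3.3.1 | Primary, target lesion | Follow-up |
| 3.3.2 | Secondary, target lesion | Follow-up |
| 3.3.3 | Primary, circuit | Follow-up |
| 3.3.4 | Secondary, circuit | Completion, variable FU.FUYDAT |

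The condition in the 3.3.4 row (circuit and device both patent) is the same as in 3.3.3; only the date differs. The variable's prefix also appears in "Did vascular access maintain patency (FU.FUVASOPYN"), and 3.3.4 calls the dates of those answers follow-up dates. So the label points to completion and the code points to follow-up.

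**Who could be affected.** Not completers. Not patients who discontinue for the reason coded Other (which includes no longer using the device), nor those whose access is no longer used: 3.3.4 counts both as events. A patient with a recovered occlusion keeps time up to the outcome date. What remains is event-free patients who leave for other reasons, and patients still ongoing at an early cut.

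**Size if the label were followed.** The plan gives no patency or attrition figure for this endpoint, and the sample-size rationale is redacted, so there is nothing to reproduce. The inputs are:
- 100 patients (Protocol section 3) and 24 months of follow-up (Protocol section 7);
- visits at days 30, 91, 183, 365 and 730 (SAP 4.4.2.3);
- assumed: true 24-month patency S of 60 to 90%, 24-month probability of early leaving d of 10 to 40%, exponential times for both;
- assumed: the redacted row is the procedure date, so affected leavers are censored at day 0.

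With affected leavers at day 0, nobody else is censored before 24 months, and Kaplan-Meier reduces to

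literal estimate = completers / (completers + events).

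*Worked case.* Take 100 patients: 20 events evenly spaced from day 36 to day 720, 20 leavers last seen patent at day 365, and 60 completers. Ten events fall by day 365.
- Censoring at follow-up: 90/100 × 60/70 = 77.1%.
- Literal label: 60/(60 + 20) = 75.0%.
- Difference: 2.1 points.

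*Closed form.* P(complete) = S(1 − d), and P(event) = [ln S / (ln S + ln(1 − d))] × [1 − S(1 − d)]. When S = 1 − d the bracketed fraction is 1/2.
- S = 0.6, d = 0.4: 0.36/(0.36 + 0.32) = 52.9%.
- S = 0.8, d = 0.2: 0.64/(0.64 + 0.18) = 78.0%.
- S = 0.9, d = 0.1: 0.81/(0.81 + 0.095) = 89.5%.

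*Simulation* (400 runs per setting). The table shows how many percentage points the literal day-0 estimate lies below the estimate censored at the last patent visit:

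| True patency | 10% leave | 20% | 30% | 40% |
|---|---|---|---|---|
| 60% | 0.9 | 1.9 | 3.2 | 4.5 |
| 70% | 0.8 | 1.7 | 2.8 | 4.1 |
| 80% | 0.6 | 1.3 | 2.2 | 3.2 |
| 90% | 0.3 | 0.7 | 1.3 | 1.9 |

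For example, 80% patency with 20% leaving gives 79.4% against 78.1%, and 60% with 40% gives 57.4% against 52.9%. The literal estimates agree with the closed form to about 0.1 point. In no run was the literal estimate the higher one. Censoring at the last visit itself lies up to about 3 points below the true value in these settings; that belongs to visit-based censoring in general, not to this label.

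**The case against.** The strongest reply is that this is a labelling or translation slip and nothing more. The variable in the disputed cell carries the follow-up prefix, the row is triggered by the patency answers, and the section has other signs of imperfect translation, such as the Japanese row heading. A program that reads FU.FUYDAT as the visit date is unaffected. This stands, and it is why no bias is claimed as shown.

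The day-0 fallback is also an inference. The row is redacted in 3.3.4, and in 3.3.3 there are redacted strings next to the procedure date, so even the model for the inference is not fully visible. That early leavers lack a completion date is likely from the separate date items but is not stated. Both points stand as limits on the size.

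A reader might infer that the reported endpoint is biased downward, or that any patency analysis before study completion would be unusable. The documents support neither. The first needs the label, not the variable, to drive the program. The second needs an interim patency analysis, and none is visible: SAP 4.2.3 mentions unfixed data only to say how uncollected items are classed. Any interim figure would also depend on a data-cut date that the plan does not give.

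Nor does the wrong endpoint name in the opening sentence change the endpoint. The heading of 3.3.4, the definitions in SAP 3.3 and Protocol 9.1(4) all identify circuit patency.

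The reply does not remove the inconsistency itself. Label and variable are both printed, so redaction does not explain it, and a stated censoring rule differs from its three counterparts.

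**Conclusion.** The inconsistency is certain; its effect is conditional. As labelled, the last termination row of 3.3.4 repeats the completion date and leaves one of the four patency endpoints without a visible follow-up-date censoring rule. Following the label would understate 24-month secondary circuit patency by about 0.3 to 4.5 points relative to censoring at the last patent visit. That range rests on assumed patency of 60 to 90%, early leaving of 10 to 40%, exponential times, leavers having no completion date, and the redacted row being the procedure date. If FU.FUYDAT is the follow-up visit date and the program uses it, the bias is zero, and the variable's prefix makes that plausible. The row should be corrected because it states a censoring rule; the opening sentence is a clerical matter.

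**What to change.** 1. In the last termination row of SAP 3.3.4, replace the completion-date label with date of follow-up (FU.FUYDAT), in line with 3.3.1 to 3.3.3.
2. Confirm that FU.FUYDAT is the follow-up visit date, and that the program for this endpoint censors event-free patients at the last follow-up with circuit and device both patent.
3. As an editorial correction, have the opening sentence of 3.3.4 refer to secondary patency of the vascular access circuit.

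The cost is two wording corrections and one program check. No new data are needed.
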